7.2.4.1. Discontinuation of Study Treatment

Reasons for discontinuation of study treatment include:

- Progressive disease, as assessed by the treating investigator in accordance with RECIST 1.1 criteria ([Appendix 3](#));
- Symptomatic deterioration (clinical progression);
 - Note: This category is applicable to patients with a global deterioration of health status requiring discontinuation of treatment. However, per RECIST 1.1 (See [Appendix 3](#)), symptomatic deterioration is not a descriptor of an objective response; it is a reason for stopping study therapy. Thus, every effort should be made to continue disease assessments per protocol until documented objective progression, regardless of any changes in therapy.
- Receipt of alternate anti-cancer treatments;
- Withdrawal request by the patient or the patient's legal representative;
 - Note: Withdrawal of consent for continued treatment should be differentiated from withdrawal of consent for study follow-up, and every effort should be made within the bounds of safety and patient choice to have each patient complete the study follow-up.
- Adverse Event, including the development of dose limiting toxicity (See [Section 8.1.6](#));
- Physician Decision;
- Non-compliance of the patient;
- Pregnancy;
- Death, otherwise not explainable by the above options;
- Patient lost to follow-up. (See below.)

Patients who discontinue CDX-011 should be seen for an End of Treatment Visit. Patients who discontinue study treatment without progression of disease as per RECIST 1.1 should continue Disease Assessment Visits until criteria for disease progression are met. (See [Table 1](#).)

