Special notes on evaluation of overall response:

- Missing assessments and inevaluable designation:
 - When no imaging/measurement is done at all at a particular time point, the patient is not evaluable (NE) at that time point.

- If only a subset of lesion measurements are made at an assessment, usually the case is also considered NE at that time point, unless a convincing argument can be made that the contribution of the individual missing lesion(s) would not change the assigned time point response. This would be most likely to happen in the case of PD. For example, if a patient had a baseline sum of 50mm with three measured lesions and at follow-up only two lesions were assessed, but those gave a sum of 80 mm, the patient will have achieved PD status, regardless of the contribution of the missing lesion.
- ‘Symptomatic deterioration’: Patients with a global deterioration of health status requiring discontinuation of treatment without objective evidence of disease progression at that time should be reported as ‘symptomatic deterioration’. Every effort should be made to document objective progression even after discontinuation of treatment. Symptomatic deterioration is not a descriptor of an objective response: it is a reason for stopping study therapy. The objective response status of such patients is to be determined by evaluation of target and non-target disease as shown in **Table 1** and **Table 2**.
- In some circumstances it may be difficult to distinguish residual disease from normal tissue. When the evaluation of complete response depends upon this determination, it is recommended that the residual lesion be investigated (fine needle aspirate/biopsy) before assigning a status of complete response. FDG-PET may be used to upgrade a response to a CR in a manner similar to a biopsy in cases where a residual radiographic abnormality is thought to represent fibrosis or scarring.
- For equivocal findings of progression (e.g. very small and uncertain new lesions; cystic changes or necrosis in existing lesions), treatment may continue until the next scheduled assessment. If at the next scheduled assessment, progression is confirmed, the date of progression should be the earlier date when progression was suspected.
- Confirmation of response: In the event of complete or partial responses, efforts should be made to obtain a confirmatory scan (no sooner than 28 days later).

Table 1: Overall response: patients with target +/-non-target disease.

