10.3.1 Primary PFS Analysis

The primary analysis of PFS will be based on the Independent Review Committee (IRC) assessment according to RECIST 1.1. Unless specified otherwise, all recorded PFS events will be included in the primary analysis regardless of stopping randomized therapy. [Table 3](#) below describes the detailed censoring rules for the primary PFS analysis. The determination of PFS is also detailed in the flow chart in the [Appendix](#) (Section 17).

Table 3: Date of Progression of Censoring for the Primary PFS analysis (IRC)

Situation	Date of Progression or Censoring	Outcome
Disease progression between scheduled disease assessments	Date of progression	Progressed
Death between scheduled disease assessment	Date of death	Progressed
Death before the first planned disease assessment at 6 weeks (plus 1 week window) without any disease assessment	Date of death	Progressed
No baseline disease assessments	Date of randomization	Censored
No post-baseline disease assessments without death before the first planned disease assessment	Date of randomization	Censored
Discontinuation of study treatment without progression (i.e., due to toxicity, withdrew consent, or lost to follow-up) and no further radiographic assessment ^a	Date of last radiological assessment without documented progression disease	Censored
Alternate anticancer treatment started without documentation of disease progression beforehand ^b	Date of last radiological assessment prior to start of further anticancer treatment	Censored
Death or disease progression after missing two or more consecutively scheduled disease assessments ^c	Date of last radiological assessment without documented progression disease prior to death/progression	Censored
Patients who have not progressed and are alive	Date of last radiological assessment without documented progression disease	Censored

a. For a patient who discontinues study treatment without PD and continues to have radiographic assessments, post-treatment radiographic assessments will be considered for PFS analyses according to the rules in this table.

b. Alternate anticancer treatment interventions that are diagnostic (e.g., biopsy) or palliative (e.g., local radiation for painful nodule) will not routinely require censoring unless they are determined to interfere with the assessment of the patients' disease status.

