10.3.3 Sensitivity PFS Analysis

Sensitivity analysis will be performed to assess potential sources of bias due to 1) censoring for alternate anti-cancer therapy; 2) symptomatic disease progression.

Alternate anti-cancer therapy prior to documentation of disease progression

It is anticipated some patients may receive subsequent anti-cancer therapy prior to documentation of progressive disease. Censoring alternative anticancer treatment prior to documented progression may be problematic since it ignores the issue of informative censoring and contravenes the basic principle of an intention-to-treat analysis. Patients who stop taking randomized study treatment prior to documented progression frequently do so due to either toxicity of the drug or due to deterioration in the status of their disease. In such cases, the investigator may judge that immediate intervention, commonly in terms of the introduction of a new cancer treatment, is in the best interest of the patient without necessarily waiting for confirmatory radiographic evidence of progressive disease ([Carroll 2007](#)).

To address the above concerns, the following sensitivity analysis will be performed: Death or disease progression that's documented after the initiation of an alternate anti-cancer therapy will be considered as a PFS event.

Symptomatic progression / hospice care events

A sensitivity analysis will be performed with symptomatic deterioration or admission to hospice care considered a PFS event with investigator's disease assessments. Patients with symptomatic deterioration will be considered to have disease progression the day after the date of the last disease assessment showing no evidence of disease progression. For patients who enter hospice care without prior symptomatic deterioration or disease progression per RECIST 1.1, the date of admission to the hospice care will be considered as PFS event date.

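### The only analysis that counts symptomatic deterioration as a PFS event uses investigator assessments, so the IRC-based primary PFS has no direct check for patients who stop for it and are not scanned again

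*Protocol*

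**What the plan says.** SAP 10.3.1 fixes the deciding analysis: "The primary analysis of PFS will be based on the Independent Review Committee (IRC) assessment according to RECIST 1.1". Protocol 7.2.4.1 lists "Symptomatic deterioration (clinical progression)" among the reasons for stopping study treatment, and Appendix 3 explains that it is not a RECIST outcome: "Symptomatic deterioration is not a descriptor of an objective response: it is a reason for stopping study therapy".

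SAP Table 3 has no row for symptomatic deterioration. A patient who stops without progression and has no further imaging is censored at the last radiological assessment. The row "Patients who have not progressed and are alive" gives the same date. If imaging continues, footnote a lets later progression count. Death counts unless two or more consecutive scheduled assessments were missed.

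SAP 10.3.3 opens: "Sensitivity analysis will be performed to assess potential sources of bias due to 1) censoring for alternate anti-cancer therapy; 2) symptomatic disease progression". Two analyses follow.

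- **Alternate therapy.** Progression or death documented after alternate therapy counts as an event. No assessor is named.
- **Symptomatic deterioration and hospice.** The analysis is run with "symptomatic deterioration or admission to hospice care considered a PFS event with investigator's disease assessments". Deterioration is dated "the day after the date of the last disease assessment showing no evidence of disease progression".

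On hospice entry the documents differ. The protocol synopsis and 12.5.1 count it as progression in the primary analysis. SAP Table 3 has no such row, and SAP 10.3.3 handles it only as a sensitivity analysis.

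**The concern.** The SAP identifies a source of bias and then examines it on a data set other than the one that decides the trial. Set against the primary analysis, the planned check changes two things together: who assesses progression, and what counts as an event. If it disagrees with IRC PFS, the cause cannot be separated. It can be compared cleanly only with the investigator PFS of SAP 10.3.2.

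Censoring at the last clean scan is informative for a patient who stopped because the disease was getting worse. The trial is open-label, so the decision to stop on clinical grounds is made by someone who knows the arm, and its frequency could differ between arms. If it does, the arm with more such stops looks better on IRC PFS than it should, and no planned analysis shows directly whether the IRC conclusion survives.

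**Working it through.** **1. The plan's own figures.** Inputs from SAP section 5: hazard ratio (HR) 4.0/6.25 = 0.64, two-sided alpha 0.05, power 85%, 2:1 allocation, 300 patients, 24 months of uniform enrolment, 10% never observed.

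- Events (Schoenfeld): (1.960 + 1.036)² / [(2/3)(1/3)(ln 0.64)²] = 8.978 / (0.2222 × 0.1992) = 203. This matches.
- Expected events at month 26: 0.9 × n × mean of [1 − exp(−λf)], with follow-up f uniform from 2 to 26 months and λ = ln 2/median. CDX-011: 0.9 × 200 × 0.720 = 129.6. Capecitabine: 0.9 × 100 × 0.833 = 74.9. The total is 204.5, which agrees with 203 at about 26 months.
- Observed HR needed for p < 0.05: exp[−1.96/√(203 × 2/9)] = exp(−1.96/6.716) = 0.747.

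**2. Who is left uncovered.** This follows a patient who stops for symptomatic deterioration without IRC progression:

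| What happens next | IRC primary analysis | Planned check on the IRC result |
|---|---|---|
| Scans continue, progression found | Event (Table 3, footnote a) | Not needed |
| Dies before missing two assessments | Event | Not needed |
| Starts other therapy, later documented progression or death | Censored before the therapy | Alternate-therapy analysis, if run on IRC data |
| No scan, no new therapy, no death in the window | Censored at last scan | None |

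The last row is the gap. Hospice entrants fall in it under SAP Table 3, but not under protocol 12.5.1.

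**3. Size.** The documents give no rate of such stops, so the shares are assumptions: the percentage of progressions that appear as deterioration with no later scan. PFS is exponential and scans follow the protocol weeks (6, 12, 18, 24, 33, 42 and so on). *Censored* means treated as in the last row above, with no deaths. *Counted* means an event the day after the last clean scan.

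| Medians, capecitabine vs CDX-011 (months) | Share, CDX-011 / capecitabine | HR, censored | HR, counted |
|---|---|---|---|
| 4.0 vs 5.2 | 5% / 5% | 0.79 | 0.79 |
| 4.0 vs 5.2 | 10% / 5% | 0.76 | 0.80 |
| 4.0 vs 5.2 | 15% / 5% | 0.72 | 0.81 |
| 4.0 vs 5.2 | 5% / 10% | 0.82 | 0.78 |
| 4.0 vs 6.25 | 5% / 5% | 0.667 | 0.667 |
| 4.0 vs 6.25 | 15% / 5% | 0.611 | 0.683 |
| 4.0 vs 6.25 | 5% / 15% | 0.731 | 0.654 |
| No difference | 15% / 5% | 0.911 | 1.020 |
| No difference | 5% / 15% | 1.087 | 0.972 |

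The 5.2-month rows are large-sample Cox estimates at a 26-month cutoff. The others average 1,500 trials of 300 patients, with 10% dropout and an assumed 28-month cutoff. Even with equal shares the HRs lie above 4.0/5.2 = 0.77 and 0.64, because progression is recorded only at scans.

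**4. Adding deaths.** The table lets no deteriorating patient die in the window, which is the extreme case. With Table 3's death rule and an assumed median survival after deterioration of 2 to 4 months, the 4.0 vs 5.2, 15% / 5% setting gives about 0.74 to 0.77 in place of 0.72. The equal-share value is about 0.79.

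**5. Dating.** Dating the event the day after the last clean scan or at the deterioration itself gave the same HR within 0.002. Both dates come before the next scan, where other progressions are recorded. The arm with more deterioration is therefore slightly penalised: 0.81 against 0.79, and 0.683 against 0.667.

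**The case against.** A reader might infer that all patients with symptomatic deterioration are censored just before progressing, and that IRC PFS is never tested for this. The documents do not support that. Protocol 7.2.4.1, 10.1.4 and Appendix 3 ask sites to keep scanning until objective progression, and Table 3 uses those scans. Deaths in the window are events. Switchers with later documented progression or death are recovered by the alternate-therapy analysis, whose rationale in SAP 10.3.3 mentions worsening disease. Comparing the planned check with the investigator PFS isolates the event definition and is indirect evidence. SAP 10.3.2 adds IRC/investigator discrepancy rates by arm, and SAP 8.1 already tabulates reasons for stopping. All of this stands, and it narrows the gap to the last row of the first table.

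A second tempting inference is that a 5% vs 15% split would decide the trial. Those shares are assumed. The HR crosses 0.747 only when the true effect lies near that threshold, and mainly when few of these patients die in the window.

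The investigator pairing is also a defensible choice. Deterioration is an unblinded site judgement, and the IRC is blinded to allocation and to investigator assessments (protocol 7.2.3), so adding it to IRC events makes a hybrid endpoint. That is why the added analysis can only be supportive. It does not remove the need for it, since the planned version cannot speak to the IRC result.

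The PFS flow chart in the SAP appendix is not shown in the text available, so a rule given only there could not be checked.

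**Conclusion.** The concern holds for a defined subgroup: patients who stop for symptomatic deterioration, have no later scan, start no other therapy and do not die before missing two assessments. They are censored at the last scan in the IRC primary analysis, and no planned analysis directly tests the IRC result for that.

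The bias is conditional. Equal shares leave the HR essentially unchanged, and the direction depends on which arm has more such stops. Under an assumed 5% (capecitabine) vs 15% (CDX-011) and medians of 4.0 vs 5.2 months, the IRC HR falls from about 0.79 to about 0.74 to 0.77 with deaths counted, or 0.72 with none. At the design medians of 4.0 vs 6.25 months it stays below 0.747 in every setting examined (0.611 to 0.731 under unequal shares), so the conclusion is unchanged. This is an inexpensive gap to close. It is not an error in the primary analysis, and the 203-event target is unaffected.

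**What to change.** In SAP 10.3.3:

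- Keep the investigator-based analysis as the companion to 10.3.2, and add the same analysis on the IRC data set: IRC progression and death per Table 3, plus symptomatic deterioration as an event. Use the primary stratified log-rank test and Cox model.
- Date the event by the existing rule, and again at the date treatment was stopped for deterioration. The second date shows whether back-dating to the last clean scan matters in the real data. The two agreed in the simulations, so expect a small penalty (about 0.01 to 0.02 on the HR) to the arm with more such events under either date, and say so when reporting.
- Tabulate by arm the patients who stopped for symptomatic deterioration without IRC progression and were censored.
- State the assessor for the alternate-therapy analysis.
- Reconcile hospice entry between protocol 12.5.1 and SAP Table 3.

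The cost is SAP wording, one table and one or two extra runs of existing programs. The reason for stopping is already collected. The added runs mix site judgements with IRC events, so they should be labelled supportive.

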Appendix 4: ECOG Performance Status

ECOG PERFORMANCE STATUS*

Grade	ECOG
0	Fully active, able to carry on all pre-disease performance without restriction.
1	Restricted in physically strenuous activity but ambulatory and able to carry out work of a light or sedentary nature, e.g., light house work, office work
2	Ambulatory and capable of all selfcare but unable to carry out any work activities. Up and about more than 50% of waking hours.
3	Capable of only limited selfcare, confined to bed or chair more than 50% of waking hours.
4	Completely disabled. Cannot carry on any selfcare. Totally confined to bed or chair.
5	Dead

* As published in Am. J. Clin. Oncol ([Oken, Creech et al. 1982](#))

Appendix 5: Cockcroft and Gault Equation

$$\text{Creatinine clearance for males} = \frac{(140 - \text{age [yrs]}) (\text{body wt [kg]})}{(72) (\text{serum creatinine [mg/dL]})}$$

Creatinine clearance for females = 0.85 x male value

Appendix 6: EORTC QLQ-C30 Questionnaire

Protocol CDX011-04: A Randomized Multicenter Pivotal Study of CDX-011 (CR011-vcMMAE) in Patients with Metastatic, GPNMB Over-Expressing, Triple-Negative Breast Cancer	Patient ID:
	Visit:

EORTC QLQ-C30 (version 3)

We are interested in some things about you and your health. Please answer all of the questions yourself by circling the number that best applies to you. There are no "right" or "wrong" answers. The information that you provide will remain strictly confidential.

Please fill in your initials:

Your birthdate (Day, Month, Year):

Today's date (Day, Month, Year):

	Not at All	A Little	Quite a Bit	Very Much
1. Do you have any trouble doing strenuous activities, like carrying a heavy shopping bag or a suitcase?	1	2	3	4
2. Do you have any trouble taking a long walk?	1	2	3	4
3. Do you have any trouble taking a short walk outside of the house?	1	2	3	4
4. Do you need to stay in bed or a chair during the day?	1	2	3	4
5. Do you need help with eating, dressing, washing yourself or using the toilet?	1	2	3	4

During the past week:

	Not at All	A Little	Quite a Bit	Very Much
6. Were you limited in doing either your work or other daily activities?	1	2	3	4
7. Were you limited in pursuing your hobbies or other leisure time activities?	1	2	3	4
8. Were you short of breath?	1	2	3	4
9. Have you had pain?	1	2	3	4
10. Did you need to rest?	1	2	3	4
11. Have you had trouble sleeping?	1	2	3	4
12. Have you felt weak?	1	2	3	4
13. Have you lacked appetite?	1	2	3	4
14. Have you felt nauseated?	1	2	3	4
15. Have you vomited?	1	2	3	4
16. Have you been constipated?	1	2	3	4

Please go on to the next page

Protocol CDX011-04: A Randomized Multicenter Pivotal Study of CDX-011 (CR011-vcMMAE) in Patients with Metastatic, GPNMB Over-Expressing, Triple-Negative Breast Cancer	Patient ID:
	Visit:

During the past week:

	Not at All	A Little	Quite a Bit	Very Much
17. Have you had diarrhea?	1	2	3	4
18. Were you tired?	1	2	3	4
19. Did pain interfere with your daily activities?	1	2	3	4
20. Have you had difficulty in concentrating on things, like reading a newspaper or watching television?	1	2	3	4
21. Did you feel tense?	1	2	3	4
22. Did you worry?	1	2	3	4
23. Did you feel irritable?	1	2	3	4
24. Did you feel depressed?	1	2	3	4
25. Have you had difficulty remembering things?	1	2	3	4
26. Has your physical condition or medical treatment interfered with your family life?	1	2	3	4
27. Has your physical condition or medical treatment interfered with your social activities?	1	2	3	4
28. Has your physical condition or medical treatment caused you financial difficulties?	1	2	3	4

For the following questions please circle the number between 1 and 7 that best applies to you

29. How would you rate your overall health during the past week?

1 2 3 4 5 6 7

Very poor

Excellent

30. How would you rate your overall quality of life during the past week?

1 2 3 4 5 6 7

Very poor

Excellent

Appendix 7: Summary of Changes

The following changes have been made to protocol CDX011-04 as Amendment 4:

SECTION(S)	CHANGE/RATIONALE
3. Protocol Synopsis, Number of Study Centers	Increased maximum number of study centers from 150 to 175 due to anticipated expansion in the EU.
3. Protocol Synopsis, Eligibility Criteria 4. Schedule of Assessments, Table 1, Footnotes 9, 11 7.2.2. Subject Eligibility	
In inclusion criteria 3 and 4 and Table 1 footnotes 9 and 11, deleted “locally advanced/recurrent/metastatic” which are examples of advanced disease settings but are not intended to be strict criteria.
 
The following statement was inserted based on the [REDACTED] recommendation following the change to Inclusion Criterion 4 in Amendment 3:
 
“Patients with low hormone receptor expression (ER and/or PR 1-9%) must be deemed appropriate candidates for cytotoxic chemotherapy by the investigator.”
 
For safety considerations added exclusion criterion 10: “Previously received capecitabine and discontinued due to progressive disease or intolerance; previously received CDX-011 (CR011-vcMMAE; glematumumab vedotin) or other MMAE-containing agents.” The original exclusion criterion 10 was deleted in amendment 2.
 
For safety considerations added exclusion criterion 11: “Active systemic infection requiring treatment. Infection controlled by oral therapy will not be exclusionary. Note: microscopic examination of urinalysis is required during screening. If urinary infection is suspected, then a negative urine culture is required prior to enrollment.” The original exclusion criterion 11 was deleted in amendment 2.
 
For safety considerations added exclusion criterion 12: “Chronic use of systemic corticosteroid above the physiologic dose (5 mg per day prednisone or equivalent) within 7 days of enrollment, except for premedication.” The original exclusion criterion 12 was deleted in amendment 2.

4. Schedule of Assessments Table 1	
Added hematology and Adverse event monitoring to Cycle 1/Day 7 and Cycle 1/Day 14 as safety measures. To minimize study burden, noted in Footnote 29 that adverse event monitoring on Cycle 1/Day 7 and Cycle 1/Day 14 could be performed in person or by telephone call, thereby moving original text in Footnote 29 to new Footnote 30. Shortened visit window of Cycle 2/Day 1 from +/-5 days to +/-3 days.
 
Footnote 17. For consistency with exclusion criterion 11, added the requirements of microscopic examination of urinalysis at baseline and negative urine culture prior to enrollment if urinary infection is suspected.
 
Footnote 21. Increased the number of patients for PBMC collection from the first 80 patients to up to 150 patients enrolled at a subset of study centers. The increase is to ensure that an adequate number of patients can provide samples from 3 time points (Cycle 1/Day 1, Cycle 2/Day 1, and End of Treatment) in order to generate sufficient and meaningful data.
 
The following statement was also added:
 
“Celldex will notify the sites when the requisite number of patients providing PBMC samples has been reached or that further data is not needed.”
 
Footnote 28. Clarified that rash biopsies are only encouraged from patients who received CDX-011 by changing “treatment-related rash” to “rash possibly related to CDX-011.”

5.4. CDX-011	Added references for the CR011-CLN-11, CR011-CLN-20, and CDX011-03 studies. Table 4. Updated table with final results from the CDX011-03 study.
8.1.7.2. Management of Toxicity	A section has been added on “Infections and Sepsis” as potential and previously observed toxicities of glembatumumab vedotin. Additional information has been included on the signs and management of infection.
9. Concomitant Therapy	For safety considerations added that prolonged use of systemic corticosteroids above the physiologic dose (5 mg prednisone or equivalent) should be avoided during the study.
Synopsis, Overview of Study Design, Statistical Methods 11. Independent Data Monitoring Committee (IDMC) 12. Statistical Considerations, 12.3 Interim Analysis	The following statements were deleted based on the [REDACTED] recommendation to remove the interim analysis of PFS: “In addition, an interim analysis of PFS will occur at 102 PFS events (50% information). The study may be stopped early if the futility boundary for PFS is met.” “...for a group sequential design with one interim analysis planned at 50% of target PFS events (102) using O’Brien Fleming alpha spending boundary.” “At the time of the interim analysis, futility will also be considered with the non-binding futility boundary for PFS defined as the observed hazard ration (HR)\geq0.90. The study may be stopped early if the futility boundary for PFS is met. The interim analysis will be performed by an independent statistical services provider in conjunction with the IDMC.” “The DMC will provide recommendations about stopping or continuing the trial based on the interim analysis...” The following section was deleted in its entirety: Section 12.3 Interim Analysis. Consequently, sample size calculations now require only 203 events (rather than 204 events) for PFS analysis and this change is reflected in the protocol.
12. Statistical Considerations, 12.5.1 Efficacy Analysis	The statement referring to the sensitivity analysis and associated references were removed as the scope of the sensitivity analysis will be specified in the Statistical Analysis Plan.
Throughout	Formatting adjustments and typographical corrections

The following changes have been made to protocol CDX011-04 as Amendment 3:

SECTION(S)	CHANGE/RATIONALE
Synopsis, Indication and Eligibility Criteria 5.5. Study Rationale 7.2.2.1. Inclusion Criteria 7.2.2.2. Exclusion Criteria	To facilitate accrual, the study population is now described as, “Patients with metastatic, GPNMB over-expressing, triple-negative breast cancer, who have failed taxane therapy and who have received anthracycline therapy or for whom anthracycline therapy is not clinically indicated.” The following eligibility criteria have also been revised accordingly: 
 • Inclusion criterion 4: Minimal or no expression of estrogen and progesterone receptors will be defined by <10% of cells positive by IHC (rather than <1%), consistent with current acceptable standards of care. • Inclusion criteria 6 and 7: The eligibility restrictions requiring “resistance” to anthracycline and taxane therapy have been removed. These eligibility criteria now read,

SECTION(S)	CHANGE/RATIONALE
	
6. Prior receipt of anthracycline-containing chemotherapy in any setting, unless anthracycline therapy is not clinically indicated, in the opinion of the treating investigator
 
7. Prior receipt of taxane-containing chemotherapy, in any setting
 
 Exclusion criterion 1: The required progression-free interval following neo/adjuvant therapy has been reduced from 6 months to 3 months

Synopsis, Overview of study design
 
7.1. Overall Design and Plan of the Study
	
In accordance with the above changes to the patient population, stratification factors have been changed from:
 
 “Resistant” to anthracycline therapy (i.e., progression-free interval of ≤ 6 months after completing treatment) vs. “Exposed” to anthracycline therapy (i.e., progression-free interval of > 6 months after completing treatment). 
to:
 
 Progression-free interval ≤ 6 months after receipt of taxane therapy vs. progression-free interval > 6 months after receipt of taxane therapy Received anthracycline therapy previously vs. no prior anthracycline therapy

Synopsis, Objectives, Overview of study design, Criteria for Evaluation, and Statistical Methods
 
6. Study Objectives
 
7.1. Overall Design and Plan of the Study
 
10.2.1.1. Anti-tumor Activity
 
12.1. Analysis Endpoints
 
12.2. Sample Size and Power Calculation
 
12.3. Interim Analysis
 
12.5.1. Efficacy Analysis
	
The primary endpoint of the study has been changed to Progression-Free Survival only, with Objective Response Rate now included as a secondary endpoint.
 
The statistical section has therefore been revised as followed:
 
 Sample size calculation is modified based on the primary endpoint of PFS with 85% power and 2-sided 5% type I error. The number of subjects (300) remains the same, but the target number of PFS events at final analysis is modified to 204. Interim analysis will be based on PFS (not ORR), and will include superiority and futility considerations. The timing of the interim analysis is determined as 50% PFS events. OS, as a secondary endpoint, will be analyzed at the interim and final analyses to support PFS and to demonstrate no detrimental effect on survival. After final analysis of PFS, patients will continue to be followed for survival and updated OS analysis maybe performed as events accumulate.
7.2.5. Completion of Study	The enrollment period is updated from 1.5 years to 2 years.
Throughout	Minor formatting and typographical changes.

The following changes have been made to protocol CDX011-04 as Amendment 2.1:

SECTION(S)	CHANGE/RATIONALE

Synopsis, Eligibility Criteria
 
7.2.2. Subject Eligibility
	
Exclusion #9 has been revised to reflect that the requirement for use of effective contraception also applies to men enrolled in the study.

SECTION(S)	CHANGE/RATIONALE
10.2.2.2. Serious Adverse Events (SAEs): Definition	Requirements for reporting of pregnancy have been revised to include reporting of cases in which a male has been exposed to the study treatments within 6 months prior to conception (paternal exposure).

The following changes have been made to protocol CDX011-04 as Amendment 2:

SECTION(S)	CHANGE/RATIONALE
2. Glossary of Abbreviations	Abbreviations re-ordered and updated.
Synopsis, Overview of study design 7.1. Overall Design and Plan of the Study	Stratification factor, “No prior chemotherapy for advanced disease vs. 1 prior line of chemotherapy for advanced disease” has been changed to “0-1 prior line of chemotherapy for advanced disease vs. 2 prior lines of chemotherapy for advanced disease”, for consistency with revised eligibility criteria.
Synopsis, Eligibility Criteria 7.2.2. Subject Eligibility	
Inclusion #1: Revised to allow for inclusion of male subjects, in accordance with [REDACTED] suggestion.
 
Inclusion #2: Further clarity regarding the definition of documented progression of disease prior to study entry is provided; “...based on radiographic, clinical or pathologic assessment showing increased tumor burden or new site(s) of disease during or subsequent to the last anticancer regimen received.”
 
Inclusion #3: Further clarity regarding definition for gpNMB expression is re-inserted; “≥ 25% of malignant epithelial cells expressing GPNMB, as determined by a central laboratory using IHC methods.”
 
Inclusion #4: Revised to allow for local determination of TNBC status, in order to facilitate patient accrual and simplify study conduct. Clarification added that laboratory reports will be required to provide quantitative results of sufficient detail to verify eligibility for all patients enrolled. Definition for HER2-negative status is also updated in accordance with recently revised ASCO/CAP guidance (Wolff, Hammond et al. 2014).
 
Inclusion #5: To facilitate accrual, the eligibility criteria have been revised to allow for 0-2 (rather than 0-1) prior chemotherapy-containing regimens for advanced breast cancer.
 
Inclusion #7: Revised to allow for inclusion of patients for whom no further taxane therapy is indicated, due to treatment-limiting toxicity to prior taxane therapy (received in any setting) or persistent comorbidities that contraindicate further therapy, in the opinion of the treating investigator.
 
Exclusion #7: Revised to clarify that, “Continued use of steroids and/or anticonvulsants (in the absence of any suspicion for progressive brain metastases) is acceptable.”
 
Exclusion #9: Detailed examples of “effective contraception” are provided as, “...double barrier contraception (e.g., condom plus spermicide in combination with a female condom, diaphragm, cervical cap, contraceptive sponge, vaginal ring or intrauterine device), intra-uterine device (IUD), implants, injectables, combined oral contraceptives, sexual abstinence (total abstinence from sexual intercourse as the preferred lifestyle of the subject; periodic abstinence is not acceptable), or sexual intercourse with only a vasectomized partner. Patients and/or partners who are surgically sterile or postmenopausal are exempt from this requirement.”
 
With consideration to [REDACTED] feedback indicating that no further QT studies are required with CDX-011, the following exclusion criteria have been deleted


SECTION(S)	CHANGE/RATIONALE
	
“10. A marked baseline prolongation of QT/QTc interval (e.g., repeated demonstration of a QTc interval >450 ms).
 
11. A history of additional risk factors for torsades de pointes (TdP) (e.g., heart failure, hypokalemia, family history of Long QT Syndrome).
 
12. The use of concomitant medications that prolong the QT/QTc interval (Appendix 6).” Appendix 6 also removed accordingly.


4. Schedule of Assessments
	
Visit windows updated to allow for up to 5 day delay in initiation of capecitabine cycles, consistent with standard of care. Randomization added to screening visit (along with footnote #25, as noted below).
 
Footnote #1: Added to facilitate study conduct, “A delay in study treatment or performance of study visits due to holidays, weekends, inclement weather or other unforeseen circumstances will be permitted and not considered a protocol violation. However, significant delays (i.e., greater than one week) should be discussed with the study medical monitor to reach consensus on subsequent scheduling.”
 
Footnote #6 (now #7): ECG, pregnancy test and EORTC QLQ-C30 are added to assessments that are not required to be repeated if performed at screening within 24 hours of Cycle 1, Day 1.
 
Footnote #7 (now #8): Revised for consistency with inclusion criterion #3 and 4, “Assessment of GPNMB expression (by IHC) will be performed at a central laboratory...Additional analyses to be performed centrally may also include...”
 
Footnote #11: Added for consistency with inclusion criterion #4, “Determination of triple-negative status will be done at a local laboratory. Tumor sample(s) used to determine eligibility must be obtained in the setting of advanced (locally advanced, recurrent or metastatic) disease. Laboratory reports will be required to provide quantitative results of sufficient detail to verify eligibility for all patients enrolled (see study entry criteria).”
 
Footnote #15 (now #17): Clarification added, “Differential should be reported consistently throughout the study as either an absolute count (preferred) or as a percentage.”
 
Footnote #20 (now #22): Text clarified to note that the mutation/molecular analyses will be performed retrospectively.
 
Footnote #25: Added for clarity, “Randomization may be performed up to 5 days prior to initiation of study treatment, but should occur only after confirming all eligibility criteria have been met.”
 
Footnote #23 (now #26): Revised to allow for study assessments to be performed within 24 hours prior to day 1 of each treatment cycle, provided that assessments remain within the specified visit window.
 
Footnote #28: Added to allow for further evaluation of treatment-related rash: “For patients who develop grade 3 treatment-related rash and who provide appropriate consent, punch biopsies and photographs of the rash site, as well as uninvolved skin, are strongly encouraged. Samples may be submitted for central analyses including quantification of gpNMB expression; in these cases, collection, processing and shipping instructions will be provided separately.”

